8.5 Co-morbidity related investigations

For participants taking anti-hypertensive medication, it will be at the local Principal Investigator's (PIs) discretion to make recommendations on anti-hypertensive drugs and diuretic in response to participants' blood pressure and weight loss outcomes. Similarly, for participants taking anti-depressant medication, it will be at the local PIs discretion to make recommendations to alter the participants' anti-depressant medication if appropriate.

8.6 Source Data

The CRF and study questionnaires are the primary data collection instruments. All data requested on the CRF will be recorded. All missing data will be explained. If the item is not applicable to the individual case then N/A will be written. All entries will be printed legibly in black ink. If any entry error has been made, to correct the error, a single line will be drawn through the incorrect entry and the correct data entered above it. All such changes will be initialled and dated. For clarification of illegible or uncertain entries, the clarification will be printed above the item and this will be initialled and dated.

A copy of the signed patient consent form and patient information leaflet will be placed in the hospital notes of all participants and in the Investigator Site File. A sticker will be placed on the cover of the notes (or inside cover) detailing the study title, contact details of the PI, participant ID and the fact that the notes should not be destroyed. All study visits and adverse events will be recorded in the hospital notes.

The PI and his/her staff must ensure that these documents are pseudonymised. Past medical history within the CRF required for inclusion in the study will be verified by participant hospital notes and/or GP medical history.

8.7 Definition of End of Trial

The end of the study is defined as the last participant's last visit.

8.8 Withdrawal of participants from the study and discontinuation of treatment

Certain circumstances will necessitate the stopping of any or all the study medication for a particular participant. Adverse event review and other safety/acceptability assessments will provide the information for the study clinician to withdraw the participant and/or discontinue the treatment drug at any time during the trial.

8.8.1 Withdrawal from the study

Participants may withdraw consent from the study before study completion if they decide to do so, at any time and for any reason. If a participant decides to withdraw from the study, this will be recorded in the study records. They will be sent a letter thanking them for their participation, and informing them that the data collected up to the time point they withdrew will be included in the study analysis and that they will not be contacted again with regards to this study. They will not be asked to attend further visits. Furthermore, we will emphasise that their standard care will not be affected by their withdrawal from this study and that they will return to standard care.

Participants will be withdrawn from this study by the research team as agreed by the PI if:

- They are diagnosed with a terminal illness
- The PI, Sponsor and or study clinician deem it unsafe for continuation in the study for medical, safety, regulatory, or other reasons consistent with applicable laws, regulations or Good Clinical Practice (GCP)
- They are considered to be lost to follow up as deemed by the clinician
- Loss of capacity during participation in research

- Treatment with medications which the PI determines to require permanent withdrawal from the study (e.g. systemic corticosteroids).

Again it will be emphasised that their standard care will not be affected by this withdrawal from the study and that they will return to standard care.

For participants who fail to return to the site, the research team should make reasonable effort to re-contact the participants (e.g., contacting participant's family or GP, reviewing available registries or health care databases) and to determine his/her health status, including at least his/her vital status. Attempts to contact such participants must be documented in the participant's records (e.g. times and dates of attempted telephone contact, receipt for sending a registered letter).

8.8.2 Treatment discontinuation (outside of the pre-specified stopping rules)

Attempts will be made to assess the primary outcome on all participants whether or not they were compliant and in those who have discontinued the treatment (including those participants who have stopped the treatment outside of the pre-specified stopping rules).

8.8.3 Permanent treatment discontinuation (outside of the pre-specified stopping rules)

Permanent treatment discontinuation is any treatment discontinuation associated with the definitive decision from the PI or the participant not to re-expose the participant to the LIRA 3mg treatment at any time. This definition is not the same as treatment discontinuation due to a participant not meeting the weight-loss targets at the pre-specified stopping rules as per the protocol.

Participants may withdraw from treatment with the investigational drug if they decide to do so, at any time and for any reason. The PI may also decide to withdraw a participant from the study based on an inability of the subject to adhere to the obligations of the study or for the safety of the participant. Items that will lead to permanent discontinuation in the study include:

- Pregnancy
- Episode of acute pancreatitis (only for participants in LIRA 3mg group)
- Breast malignancy (only for participants in LIRA 3mg group)
- They repeatedly violate or are non-compliant with the protocol
- Where LIRA 3mg doses are not tolerated by the participant
- Any other contraindication to the study medication which the PI determines to require permanent treatment discontinuation.

*Please note if a participant's amylase result is within the normal range but the study clinician suspects acute pancreatitis a lipase test will be conducted.

All efforts should be made to document the reasons for treatment discontinuation and this should be documented in the CRF and medical records.

Any abnormal laboratory value that in the opinion of the clinician may be an indication for discontinuing the treatment of a participant will be rechecked by the PI or second clinician if the first clinician is the PI for confirmation before making a decision of permanent discontinuation of the investigational drug for the concerned participant. Threshold values for the discontinuation of investigational drug use shall be defined in collaboration with the Sponsor representative. The values will be adapted to the population studied, as appropriate.

8.8.4 Handling of participants after permanent treatment discontinuation

This study observes the effect of a targeted prescribing pathway (i.e. the use of LIRA 3mg when stopping rules are applied in combination with standard care in a Tier 3 service for patients with severe and complex obesity) compared with standard care alone. In case the GP or PI stops treatment or a participant withdraws from treatment with LIRA 3mg, e.g. for safety reasons, the participant will be offered standard care and the observation will continue.

If LIRA 3mg is stopped for other reasons not related to the applied stopping rules, it should be determined whether the stop can be made temporarily; permanent discontinuation of LIRA 3mg should be a last resort. Any discontinuation of the drug for reasons not related to the stopping rules should be fully documented in the CRF and medical records.

Participants must be instructed to notify the Investigator immediately if they become pregnant during the trial. Pregnancy will result in permanent treatment discontinuation (this will apply to both the LIRA 3mg and the standard care groups). The Investigator must report any pregnancy during the study to Novo Nordisk except for pregnancies occurring in the screening period prior to study treatment. Participants will give consent on enrolment that the Investigator will report any pregnancy during the study to Novo Nordisk and they will be asked to provide information about the pregnancy, delivery and the health of her infant until one month of age. Any AE in the child will be reported.

Participants will be followed according to the study procedures as specified in this protocol up to the scheduled date of study completion. If possible, and after the permanent discontinuation of investigational drug, the participants will be assessed using the procedure normally planned for the last onsite visit, if appropriate. All cases of permanent treatment discontinuation should be recorded by a member of the research team in the appropriate pages of the CRF and medical records when considered as confirmed. Study Sponsor is to be informed.

8.8.5 Handling of participants after temporary treatment discontinuation

Temporary discontinuation of LIRA 3mg may be considered by the PI because of suspected Adverse Events (AEs). A rationale (e.g. severe nausea and vomiting, other gastrointestinal symptoms) must be given in writing by the PI.

Re-initiation of treatment with LIRA 3mg may be done at a lower dose, under close and appropriate clinical/and or laboratory monitoring once the PI has considered, according to their best medical judgment, that the possible responsibility of the LIRA 3mg in the occurrence of the concerned event was unlikely and if the inclusion and exclusion criteria for the study are still met.

For all temporary treatment discontinuations, the duration of treatment discontinuation should be recorded by the research team when considered as confirmed.

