7.2 Inclusion Criteria

To be considered eligible to participate in this study, a patient must:

- be aged between 18-75 years old (inclusive)
- understand written and spoken English
- be able to give informed consent
- have a BMI ≥ 35 kg/m 2
- have been referred to the Tier 3 service in one of the participating sites
- have a stable body weight (less than 5kg self-reported change during the previous 12 weeks)
- have at least one of prediabetes, diabetes, hypertension, and/or obstructive sleep apnoea, as defined below:
 - prediabetes (defined as established diagnosis of impaired fasting glycaemia (IFG) from GP and/or established diagnosis of impaired glucose tolerance (IGT) from GP and/or HbA1C 42-47 mmol/mol (6-6.4%) without glucose lowering medications, at a blood test during the last 6 months)
 - diabetes (defined as established diagnosis of Type 2 diabetes from GP and/or HbA1C ≥ 48 mmol/mol ($\geq 6.5\%$) at a blood test during the last 6 months] and/or being treated with any combination of lifestyle, metformin, sulphonylureas, Thiazolidinediones (TZDs) or SGLT-2)
 - hypertension treated (defined as being on antihypertensive treatment with or without a diagnosis of hypertension from GP) or untreated (defined as Systolic Blood Pressure ≥ 140 mmHg at two consecutive visits at the Tier 3 clinic),
 - obstructive sleep apnoea (on CPAP or established diagnosis of Apnoea Hypopnoea Index ≥ 15 at sleep studies during the last 12 months).

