7.3 Exclusion Criteria

Patients who have met any of the following criteria will be excluded from the study:

- Diagnosis of Type 1 diabetes
- T2DM on treatment with DPP-IV or insulin currently

- Treatment with GLP-1 receptor agonists within the last 6 months and/or have a history of GLP-1 receptor agonist intolerance
- Treatment with anti-obesity drugs within 12 weeks prior to randomisation
- eGFR $\leq 30\text{ml}/\text{min}/1.73\text{m}^2$ on serum testing over the last 26 weeks
- Females referred to the clinic because of fertility problem
- Females of child bearing potential who are pregnant, breast-feeding or intend to become pregnant or are not using or willing to use adequate contraceptive methods (as described in Section 8.3.1)
- Have terminal illness
- Are not primarily responsible for their own care
- Any other significant disease or disorder which in the opinion of the investigator, may either put the participants at risk or may influence the result of the study or the participant's ability to participate
- Untreated or uncontrolled hypothyroidism/hyperthyroidism defined as thyroid-stimulating hormone, as defined by local sites pathology laboratory reference ranges as outside the normal range; mIU/litre (see local site laboratory reference ranges)
- Family or personal history of multiple endocrine neoplasia type 2 (MEN2) or familial medullary thyroid carcinoma (FMTC)
- Personal history of non-familial medullary thyroid carcinoma
- History of chronic pancreatitis or idiopathic acute pancreatitis
- Amylase levels three times higher than the upper normal range
- Obesity induced by other endocrinologic disorders (e.g. Cushing's Syndrome)
- Current or history of treatment with medications that may cause significant weight gain, within 12 weeks prior to randomisation, including systemic corticosteroids (except for a short course of treatment, i.e. 7–10 days), atypical antipsychotic and mood stabilizers (e.g. clozapine, olanzapine, valproic acid and its derivatives, and lithium)
- Initiation of antidepressants during the last 12 weeks
- Previous surgical treatment for obesity <1 year before trial entry weight loss procedures/surgery including removal of a gastric band and/or gastric balloon
- History of other severe psychiatric disorders
- History of known or suspected abuse of alcohol and/or narcotics
- History of major depressive episode during the last 2 years

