8.3 Data Collection Visits (Baseline, Weeks 52 and 104)

Eligibility criteria for each participant will be re-checked at every visit.

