- Participants on LIRA 3mg who did not reach the target of $\geq 15\%$ weight loss will meet the study clinician who will explain to them that they cannot continue on the medication any longer and that they will instead continue in the study on the Tier 3 programme with standard care. These participants will remain in the intervention group (targeted prescribing pathway), but will not receive LIRA 3mg as per the pre-specified stopping rules.

The purpose of the long-term (52-104 weeks) follow-up is to examine whether LIRA 3mg will help the “early and good” responders to maintain weight loss $\geq 15\%$ in comparison with the control group over a longer period of time. Additional procedures at the **Week 104** visit for all participants will include:

- The study clinician at each site will assess all the patients who participated in the study that have not been referred for bariatric surgery
- Participants who had significant weight regain during the second year in either treatment group will be discussed in Tier 3 MDT and may include a recommendation to their GP to refer them to Tier 4 service for bariatric surgery
- For participants who are on LIRA 3mg: the clinician will make a recommendation to the participant’s GP as to whether or not they should continue on the medication long-term, pending the local prescribing guidelines. Please note: participants on LIRA 3mg targeted prescribing pathway will only receive study medication for a maximum of 106 weeks (4 weeks titration, 100 weeks at 3mg, +/- 2 weeks visit window). For those participants that achieve more than 15% weight loss or a BMI $< 35\text{kg/m}^2$ prior to the 104 weeks, treatment with LIRA 3mg will be continued unless the patient begins to experience side-effects.

In an attempt to aid retention for the primary end point (week 52 – V11) all participants will be offered an incentive payment of £25 that will be paid on completion of the week 52 (visit 11) and dependant on us having weight data for that visit.

In response to the COVID19 global pandemic an interim time point for the quality of life questionnaires has been added (HSRUQ, TSQM, EQ-5D, IWQOL-Lite, IPAQ-Long and PHQ-9). These will be sent out to all participants during the COVID19 pandemic.

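### The rule for restarting LIRA after a pause relies on the study's entry criteria without saying which still apply after randomisation, so it can bar restart in some responders and conflicts with other sections

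*Protocol*

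**What the plan says.** Protocol section 8.8.5 covers temporary stops for suspected adverse events. Its examples of a reason to pause are severe nausea and vomiting and other gastrointestinal symptoms. Restart, possibly at a lower dose, has two conditions: the investigator must consider that LIRA's responsibility for "the occurrence of the concerned event was unlikely and if the inclusion and exclusion criteria for the study are still met". No criterion is exempted.

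Three entry criteria that bear on a treated participant carry no link to the date of randomisation:

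- Section 7.2: "have a BMI ≥ 35 kg/m 2".
- Section 7.2: "have a stable body weight (less than 5kg self-reported change during the previous 12 weeks".
- Section 7.3 excludes "Treatment with GLP-1 receptor agonists within the last 6 months and/or have a history of GLP-1 receptor agonist intolerance".

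By contrast, the section 7.3 exclusion for earlier anti-obesity drugs is tied to the period before randomisation.

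Section 8.3 adds "Eligibility criteria for each participant will be re-checked at every visit". Section 8.4 and the inclusion/exclusion row of Appendix 3 repeat this for the other visits.

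Other sections bear on the same decision:

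- Section 8.8.4: "permanent discontinuation of LIRA 3mg should be a last resort".
- Section 8.3.2, for participants who pass 15% loss or fall below BMI 35: "prior to the 104 weeks, treatment with LIRA 3mg will be continued unless the patient begins to experience side-effects".
- Section 9.1 bases recommencing after a contra-indicated procedure on individual safety assessment and does not mention entry criteria.
- Sections 8.3.1.2, 8.8.3 and 9.2 take participants off LIRA when doses are not tolerated.
- Section 14.10.1 names gastrointestinal effects as the most frequent adverse effects of LIRA and says they usually diminish on continued treatment.

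The SAP does not address eligibility for restart.

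**The concern.** The entry criteria describe a patient before treatment: above a BMI threshold, stable in weight and not recently on a drug of this kind. The pathway sets out to change the first two. A restart rule that asks whether those criteria remain satisfied can therefore turn against a participant because treatment is working.

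The causality condition has a similar difficulty. The events offered as typical reasons to pause are the ones the protocol itself most associates with LIRA, so a finding that LIRA was unlikely to be responsible may often be hard to make.

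Two things are at stake. First, the five sites may read the clause differently and so deliver different versions of the intervention. Second, some participants could leave drug for a reason outside the three weight-loss stopping rules in section 6.2, which are the feature of the pathway under test. That could affect the week-52 comparison and the number still on drug when week-104 maintenance is assessed.

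**Working it through.** The restart clause contains no figure to reproduce. The check is whether meeting the pathway's own targets can breach the entry criteria, followed by a comparison of the sections.

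**Inputs.** BMI of at least 35 and less than 5 kg change in 12 weeks (section 7.2); the GLP-1 receptor agonist exclusion (section 7.3); targets of 5%, 10% and 15% loss at weeks 16, 32 and 52 (section 6.2).

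**BMI.** After a fractional loss L, BMI is baseline × (1 − L). It is below 35 when baseline BMI is below 35/(1 − L):

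- 5% loss: 35/0.95 = 36.8
- 10% loss: 35/0.90 = 38.9
- 15% loss: 35/0.85 = 41.2

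A participant starting at BMI 40 has 40 × 0.85 = 34.0 after 15% loss and fails. One starting at 42 has 35.7 and one starting at 45 has 38.25; both pass.

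**Weight stability.** Suppose loss is at a steady rate and the target L is just met at week t. The loss per 12 weeks is then w × L × 12/t for baseline weight w. It reaches 5 kg when w = 5t/(12L):

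- Week 16, 5%: (5 × 16)/(12 × 0.05) = 133.3 kg
- Week 32, 10%: (5 × 32)/(12 × 0.10) = 133.3 kg
- Week 52, 15%: (5 × 52)/(12 × 0.15) = 144.4 kg

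Faster or front-loaded loss breaches the criterion at lower weights. A participant whose weight has levelled off passes.

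**Both together.** A participant of 120 kg and BMI 42 who loses 10% by week 32 has BMI 42 × 0.90 = 37.8 and loses 120 × 0.10 × 12/32 = 4.5 kg per 12 weeks. Both weight criteria are met, so on these two criteria the clause catches some responders and not others.

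**GLP-1 exclusion.** If the study drug counts as a GLP-1 receptor agonist, every participant dosed in the last 6 months fails, responder or not. This is an assumption. SAP section 5.4.4 refers to GLP-1 at a glucose-lowering dose, which is consistent with it but does not state it.

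**The sections side by side.**

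- 8.8.5 against 8.8.4: one makes permanent stopping a last resort; the other can make it the outcome of a pause through criteria that response or dosing breaches.
- 8.8.5 against 9.1: two routes back onto drug, one with an entry-criteria test and one without.
- 8.8.5 against 14.10.1: the causality condition sits badly with the gastrointestinal examples.
- 8.8.5 against 8.3.1.2, 8.8.3 and 9.2: restart at a lower dose is allowed in one place, and withdrawal from LIRA for doses not tolerated is required in the others. The boundary between the two situations is not drawn.
- 8.8.5 against 8.3.2: the latter continues LIRA below BMI 35 but excepts side-effects.

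**Downstream in the SAP.** Appendix 7 measures days on LIRA up to the last known date of use. A participant who meets the week-16 and week-32 weight targets but is refused restart can fall below 70% of the days to week 52, and so leave the per-protocol set (section 3.3.3).

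**The case against.** The best counter-argument is that nobody would apply the clause literally. A literal GLP-1 exclusion would fail every dosed participant at the first re-check, yet the protocol plainly means responders to stay on drug and governs continuation by the stopping rules. Failing a re-check is not listed as a reason for withdrawal in section 8.8.1 or for permanent discontinuation in section 8.8.3. This has force as to intent. But section 8.8.5 does attach a consequence to the criteria, and no section says which of them lapse, so each site has to decide.

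Several narrower objections stand:

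- A reader might infer that responders cannot meet the criteria. The arithmetic above shows that many can.
- A reader might infer that the clause singles out responders. The one potentially universal bar, the GLP-1 exclusion, applies equally to non-responders and rests on a drug-class assumption. SAP section 15.2 treats LIRA 3 mg as an obesity medication, and the anti-obesity-drug exclusion is tied to randomisation.
- Section 8.3.2 does not flatly contradict 8.8.5. Its exception for side-effects may cover the very participants who paused for a suspected adverse event.
- Not every pause becomes permanent. Section 9.1 allows recommencing without an entry-criteria test.
- Doses not tolerated and an event later judged unlikely to be due to LIRA can be separate situations.
- Much is already recorded: the rationale and duration of a pause (8.8.5), reasons for discontinuation (8.8.3 and 8.8.4), and reasons for stopping in the CONSORT diagram (SAP section 5.1). Only the restart decision is missing.

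**Conclusion.** The point holds as a conflict of wording with a possible effect on delivery of the intervention. Read as written, section 8.8.5 can bar restart in responders below the BMI thresholds shown or losing 5 kg or more in 12 weeks, and, under the drug-class assumption, in anyone recently dosed. That is inconsistent with section 8.8.4 and differs from section 9.1. Section 8.3.2 points the same way as 8.8.4, subject to its exception for side-effects. The weight-stability thresholds assume loss at a steady rate.

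The effect on the primary result cannot be sized. A reader might assume that 10% to 20% of the intervention arm pause, that none restart, and that all of them then have the 5% control rate. The planned 16% would become 16 − 0.10 × (16 − 5) = 14.9% to 16 − 0.20 × (16 − 5) = 13.8%. The documents support none of those three assumptions, and 14.9% lies within the 14% to 20% range that section 11.2 already considers likely. These figures should not be read as an estimate.

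It is more than missing detail, because a stated rule produces the conflict. No view is taken on which clinical rule should prevail.

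**What to change.** Reconcile section 8.8.5 with sections 8.3, 8.3.1.2, 8.3.2, 8.4, 8.8.3, 8.8.4, 9.1 and 9.2 and with the inclusion/exclusion row of Appendix 3. The sponsor's clinicians should decide how the passages are to agree, and state in section 8.8.5 and in the visit re-checks which criteria apply after randomisation and which apply at entry only. The same revision should address how the causality condition relates to the gastrointestinal examples.

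Add one CRF item recording whether restart was allowed after a pause and, if not, why. Stops arising from a refused restart can then be counted separately from those due to the weight-loss rules.

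The cost is a protocol wording amendment and one CRF item, with no extra participants or visits.
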